**Circadian Rhythms: Results (N = 410)**

**Circadian Rhythms: Results (N = 410)**

intervention not only significantly improved SQI and secondarily, insomnia, wake after sleep onset, and sleep efficiency, but the yoga participants decreased their sleep medication use during the intervention, while the control participants increased sleep medication use.

Multi-oscillator modeling revealed a 12-hour, ultradian rhythm model fit the circadian activity rhythms better than a single-oscillator, 24-hour model and demonstrated significant rhythm differences between groups post-intervention ( $p < 0.05$ ) with a delayed 12-hour acrophase in the yoga group ( $p < 0.05$ ). The yoga group demonstrated higher physical activity during the morning (first 12 hours of the day) and stabilized physical activity throughout the afternoon and evening (second 12 hours of the day); whereas, the standard care control group showed a lower physical activity pattern in the morning and a higher peak in physical activity in the afternoon and evening. Blunted morning circadian rhythms (low physical activity) and excessive peaks (high physical activity) in circadian rhythms during the afternoon and evening are associated with SQI.

Adherence and Adverse Events: Survivors assigned to the yoga arm attended an average of 6.5 of the 8 prescribed sessions for a total of 480 minutes of the prescribed 600 minutes during the 4-week intervention period. Survivors in the yoga arm also reported extra yoga practice outside of the two required yoga sessions, resulting in a total average of 182 minutes each week over 3 days with a rating of perceived exertion of 3.4 (moderate intensity). Contamination in the control condition was very low; 7 participants reported an average of 20 minutes of yoga one time each week with a rating of perceived exertion of 1.0 (very weak) during the intervention period. There were no study-related adverse events. Survivors liked the yoga intervention; 100% found it useful for improving their sleep and would recommend it to other cancer survivors.

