7.4 **Objective Insomnia Symptoms** will be measured via actigraphy. Participants will have their sleep-wake exposure monitored through the use of a wrist-worn actigraphy-based data logger, the Actigraph GT3X manufactured by ActiGraph LLC, Pensacola, FL. The Actigraph GT3X features a variable epoch length that can be set, and has 16MB of non-volatile memory. “Non-volatile” means that even if the battery, which can log 21 days of runtime before needing to be recharged, becomes exhausted, the data remain intact. The motion data will be analyzed using the ActiLife Analysis Software. The program uses a validated sleep algorithm to provide an assessment of sleep by delineating the “in bed” and “out of bed” portions of the day. The software and algorithms calculate the percent of sleep during these two portions of the day. The actigraphy, in conjunction with the sleep/wake diaries, can be used to approximate the timing of both daytime and nighttime sleep. While daily sleep diaries are a common method used to examine patterns of sleep and wakefulness, we will internally validate the at-home monitoring by comparing actigraphy data collected during baseline and follow-up to the daily questionnaires. This measurement strategy allows for an assessment of sleep problems (sleep latency, WASO, sleep efficiency, daytime sleep) which is free from either subjective or observer bias and requires minimal subject compliance, allows for the detection of periods of wakefulness as brief as 30 seconds in duration.

7.5 **Circadian Activity Rhythm** will be assessed using actigraphy. The exact actigraphs used to objectively assess sleep described in section 7.4 will be used. A two-oscillator cosinor model (12 and 24 hours) will be calculated using nonlinear regression methods on the log (activity counts). This model was found to fit the data for cancer survivors (Study 3) better than a single-oscillator model. Mesor (overall), Amplitude, and Acrophase for the 12- and 24-hour cycles will be calculated.

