- 10.6.2 **Missing Values.** Every effort will be made to facilitate participants' completion of questionnaires and provision of actigraphy and physical function data, and blood. In the event of missing data, the reasons for missing data will be recorded and tabulated according to treatment group. Some missing data are inevitable. Under the missing at random (MAR) assumption, we will use multiple imputation to obtain unbiased estimates of key parameters. If data are suspected to be missing not at random (MNAR), a sensitivity analysis using the methods of Liublinska and Rubin (2014) will be run to determine the impact on results. If the estimates are similar to the ones obtained from the simpler analysis of only complete cases, we will report the complete-case analysis results.
- 10.7 **Statistical Analyses:**
- 10.7.1 **Primary Aim 1 Analyses:** To determine if YOCAS® is as effective as CBT-I and more effective than health education for improving **insomnia (ISI total)**, two separate analyses will be performed, each aimed at estimating the difference between arms in mean change from baseline with associated confidence intervals. The comparison of YOCAS® to CBT-I is a non-inferiority hypothesis with a one-sided alpha, and the comparison of YOCAS® to the health education control is a traditional null hypothesis of no difference with a two-sided alpha. See the Statistical Power section for more details. A linear mixed effects ANCOVA will be used to assess the statistical significance of the differences in mean changes from baseline for the two groups (Hypothesis 1 = YOCAS® vs. CBT-I;

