Hypothesis 2 = YOCAS® vs. health education). **The response will be post-treatment ISI total score.** The model fixed effects will be Group and Baseline ISI. NCORP Site will be included as a random effect. The REML method will be used to estimate the random effect variance components. If the NCORP Site variance component is significant, the fixed effects will be tested using F tests with the Kenward-Roger degrees of freedom adjustment. If the NCORP Site variance component is not statistically significant, we will use ordinary least-squares estimation and F-Tests for testing the fixed effects. The mean difference between groups with associated 95% confidence intervals will be estimated using the appropriate contrasts. An alpha level of 0.025 will be used to adjust for multiple comparisons. Additional follow-up analyses will include NCORP site and cohort as covariates and examine possible interactions.

- 10.7.2 **Secondary Aim 2 Analyses:** To examine if YOCAS® is effective for improving **objective symptoms of insomnia** (sleep latency, sleep efficiency, wake after sleep onset, sleep duration, and daytime napping via actigraphy) and **global sleep quality impairment** (PSQI total) compared to CBT-I and a health education control, we will use the same methods as for Primary Aim 1 with no multiple comparison adjustments.

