- 10.7.4 **Exploratory Mechanistic Aim 4 Analyses:** To explore whether YOCAS® is effective for improving **circadian activity rhythms (24 and 12 hour amplitudes and acrophases via actigraphy), physical function (i.e., cardiopulmonary [6-min. walk] and muscular function [dynamometry]), and inflammation (IL-6, IL-8, IL-10, IL-1 $\beta$ , IFN- $\gamma$ , & TNFR1 via standardized ELISAs and multiplexes)** compared to CBT-I and a health education control, we will use the same analytical methods as for Primary Aim 1 to assess changes in the estimated parameters of the two-oscillator (12 and 24 hours) cosinor model and the Hill function model. These parameters include **Mesor (M), Amplitude (A1) and Acrophase (Phi1) for the 24-hour oscillator and Amplitude (A2) and Acrophase (Phi2) for the 12-hour oscillator.** Estimates will be from the log-transformed activity counts using nonlinear regression. Degree of rhythmicity will be assessed with the Fisher-transformed model multiple correlation. We will also fit single-oscillator models (24-hour Mesor, Amplitude, and Acrophase) for comparison with other published studies. The time participants woke up in the morning and fell asleep in the evening will be extracted from weekly diaries. We will apply the same methods as for physical function and inflammation outcomes; inflammatory biomarkers will be log-transformed as needed.
- 10.7.5 **Exploratory Mechanistic Aim 5 Analyses:** To explore **whether changes in physical function, circadian rhythm and inflammation mediate the effect of YOCAS® on insomnia,** we will use separate mediation analyses performed on pre-post ISI change scores (CS) and the above outcomes as potential mediators. Path analysis will be used, where the intervention affects CS, the intervention affects the mediator, and the mediator, in turn, affects the CS. We will also use structural equation modeling. Mediation will be assessed via indirect effect estimation using bootstrap-based 95% confidence intervals. Latent variables will be introduced into the model for multiple measures of a common entity (e.g., cytokines for inflammation). If multiple measures are weakly correlated, we will split them

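### Section 10.7.4 analyses acrophase by linear ANCOVA with no stated phase reference; if fitted phases lie near the branch cut, the estimated shift, chiefly in the 12-hour acrophase, can shrink or change sign

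*Combined protocol and SAP*

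**What the plan says.** Section 10.7.4 names as outcomes "circadian activity rhythms (24 and 12 hour amplitudes and acrophases via actigraphy". It sends the fitted cosinor parameters to the Primary Aim 1 method ("we will use the same analytical methods as for Primary Aim 1 to assess changes in the estimated parameters of the two-oscillator" cosinor model), and those parameters include "Amplitude (A2) and Acrophase (Phi2) for the 12-hour oscillator" as well as the 24-hour acrophase Phi1.

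Section 10.7.1 defines that method: "A linear mixed effects ANCOVA will be used to assess the statistical significance of the differences in mean changes from baseline". The response is the post-treatment value, "The model fixed effects will be Group and Baseline ISI", and site is a random effect. Carried over to acrophase, this is a straight-line regression of post-treatment phase on group and baseline phase.

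On how the phase is obtained, section 10.7.4 says "Estimates will be from the log-transformed activity counts using nonlinear regression", and section 7.5 says "Mesor (overall), Amplitude, and Acrophase for the 12- and 24-hour cycles will be calculated". Neither gives a range, a reference time or an unwrapping rule for the phase, and neither mentions circular statistics or the cosine and sine coefficients.

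The general safeguards are in section 10.6.1: normality checks, unspecified transformations for skewness, Box-Cox for unequal residual variance, a Wilcoxon test on change scores as a last resort, and outliers that are investigated but kept in the final analysis. Section 10.7.5 takes the circadian outcomes forward as candidate mediators.

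**The concern.** Acrophase is a clock time on a circle. On the 12-hour cycle, a participant who moves from 11.5 h to 0.5 h has been delayed by 1 h, but plain subtraction gives 0.5 - 11.5 = -11 h. A linear model treats the two ends of the scale as far apart when they are adjacent. A true delay near the cut pushes more of the yoga arm over the end of the scale, and each such participant is then scored as a large advance.

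Direction is the quantity of interest here. The account of the prior trial in section 2.0 reports a rhythm difference "with a delayed 12-hour acrophase in the yoga group". A method that can turn a delay into an advance could mask or contradict a replication of that finding, and the mis-scored values would pass into the mediation paths of section 10.7.5.

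**Working it through.** **No figure to reproduce.** The documents give no power, mean, SD or effect size for acrophase. The 168 per arm and r = 0.576 used below belong to the ISI calculation in section 10.2.1. They are consistent there: 4.6 × √(1 - 0.576²) = 3.76, and 2 × (1.96 + 0.842)² × 3.76² / 1.15² ≈ 168 per arm. They are borrowed here only to set a scale.

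**Assumed inputs.** True yoga delay δ = +0.5 h; phase stored on 0 to P with P = 12 h; phase roughly normal before wrapping, with SD 1, 1.5 or 2 h; mean phase varied.

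**Formula.** Randomisation makes baseline wrapping equal between arms in expectation, so the linear estimate averages the difference in stored post-treatment means:

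E(linear) = δ - P × (p_yoga - p_comp) + P × (q_yoga - q_comp),

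where p is the share of each arm above P and q the share below 0, before wrapping.

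**Worked case: mean 11 h, SD 1 h.** p_comp = Pr(Z > 1) = 0.1587, p_yoga = Pr(Z > 0.5) = 0.3085, q negligible. E(linear) = 0.5 - 12 × 0.1498 = -1.30 h.

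**Worked case: mean 9 h, SD 2 h.** p_comp = Pr(Z > 1.5) = 0.0668, p_yoga = Pr(Z > 1.25) = 0.1056. E(linear) = 0.5 - 12 × 0.0388 = 0.03 h.

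The table gives the formula value, with the average from simulated trials in brackets (168 per arm, r = 0.576, site effect omitted).

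| Mean phase | SD 1 h | SD 1.5 h | SD 2 h |
|---|---|---|---|
| 3 h | 0.49 (0.49) | 0.35 (0.35) | 0.18 (0.2) |
| 6 h | 0.50 (0.51) | 0.50 (0.49) | 0.47 (0.48) |
| 9 h | 0.44 (0.44) | 0.20 (0.19) | 0.03 (0.04) |
| 10 h | -0.03 (-0.02) | -0.31 (-0.30) | -0.32 (-0.31) |
| 11 h | -1.30 (-1.31) | -0.90 (-0.89) | -0.61 (-0.62) |
| 12/0 h | -1.80 (-1.81) | -1.07 (-1.05) | -0.68 (-0.69) |

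At a mean of 11 h the simulated estimate had the wrong sign in 99.8%, 97% and 91% of trials (SD 1, 1.5, 2 h), and was significant in the wrong direction in 80%, 46% and 28%.

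**After recentring** each phase on the pooled baseline circular mean, the same ANCOVA gave +0.46 to +0.51 h wherever the mean lay. Power was about 1.00 at SD 1 h, 0.95-0.97 at SD 1.5 h and 0.70-0.75 at SD 2 h.

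**24-hour acrophase (P = 24).** With a mean of 14-16 h the share beyond either end is at most about 0.0001, and the formula gives 0.50 h at every SD. Simulation gave +0.49 to +0.51 h. Only a mean close to midnight matters: at 20 h the formula gives 0.36 h (SD 1.5 h) and 0.09 h (SD 2 h); simulation gave 0.37 and 0.07.

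**Fallback test.** With the mean 1 h before the cut, the Wilcoxon test on change scores rejected in 5-6% of simulated trials at SD 1-2 h, against 72-100% for the recentred ANCOVA. It does not recover the lost information.

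**The case against.** A reader might infer that the plan commits the sponsor to a wrong analysis, or that the sign will reverse in this trial. The documents support neither. Storage on 0-12 h is an assumption; the plan says only that the phase comes from nonlinear regression, and a fitted phase need not be reduced to that range. When an unconstrained two-oscillator model was fitted to 150 simulated weeks with true phase around 12/0 h, a common start value of 0 h put 148 of the 150 estimates on one continuous branch, whereas start values of 3 h or 6 h mixed branches. So the outcome depends on an implementation choice that the plan leaves open. That limits the claim to a possibility, but it is also the reason to state the convention in advance: the choice can decide the sign of the estimate.

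A reader might also infer that linear analysis is safe only when phases sit mid-cycle. That is too strong. At SD 1 h with the mean 3 h from the cut, the linear estimate is still 0.44-0.49 h. Nor does the 24-hour acrophase carry the same risk, as shown above.

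Section 10.6.1 requires assumptions to be checked and outliers to be investigated, and jumps of about 11 h on a 12-hour scale would be conspicuous. That stands as detection. It is not a cure, because none of the named remedies restores the circular order and extreme values stay in the final analysis. A careful analyst would probably unwrap the phases anyway, but the plan does not require it.

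Finally, no mediation model was simulated, so harm to Aim 5 is inferred from its use of the same outcomes and has not been measured.

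**Conclusion.** The point holds as a conditional one. Section 10.7.4 applies a linear model to a circular quantity without fixing the phase reference, and the estimated shift in the 12-hour acrophase can be attenuated or reversed if fitted phases fall near the cut. For an assumed true delay of +0.5 h, the linear estimate averages -1.3 to -0.6 h with the mean 1 h before the cut (SD 1-2 h). With the mean 3 h from the cut it ranges from about 0.49 h (SD 1 h) to 0.04 h (SD 2 h, mean 9 h). It is essentially unbiased when the mean lies several SDs away.

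Every acrophase input is assumed: delay, correlation, storage range, SD and location. The prior trial supplies a direction but no size. The figures show what could happen and do not estimate the bias in this trial. The ISI primary result and the secondary aims are untouched, so this is a low-severity improvement to exploratory analyses.

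**What to change.** Add to section 10.7.4 that each acrophase is expressed, before ANCOVA, as its signed circular deviation in (-P/2, P/2] from the pooled baseline circular mean, with P = 12 or 24 h. Alternatively, state that the cosine and sine coefficients of each oscillator are analysed jointly. State in section 10.7.5 that the mediation models use the same recentred values.

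The cost is a sentence or two of SAP text and a few lines of code. Data collection and sample size do not change. Because the reference is computed from baseline data pooled over arms, it can be fixed without sight of any treatment comparison.

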## 11.0 Records To Be Kept

Measure	Screening	Baseline	Mid-Point Intervention	Post-Intervention	3 Month Follow-Up	6 Month Follow-Up
Eligibility and Consent		✓				
DSM-V	✓					
Insomnia Severity Index Screening	✓					
On-Study Data/Participant Interview		✓				
Clinical Record Information		✓				
Cancer Treatment Notes		✓				
Sleep Medication and CAM Use		✓	✓	✓	✓	✓
Stimulant Medication and CAM Use		✓	✓	✓	✓	✓
Insomnia Severity Index (ISI)		✓	✓	✓	✓	✓
Sleep Quality (PSQI)		✓	✓	✓	✓	✓
Sleep Chronotype (MEQ-SA)		✓	✓	✓	✓	✓
Actigraphy		✓	✓	✓	✓	✓
6-Minute Walk Test		✓	✓	✓	✓	✓
Handgrip Dynamometer Test		✓	✓	✓	✓	✓
Fasting Blood Draw (Blood Requisition Form)		✓	✓	✓	✓	✓
Symptom Inventory (SI)		✓	✓	✓	✓	✓
Fatigue Interference (BFI)		✓	✓	✓	✓	✓
Cancer-Related Fatigue (FACIT-F)		✓	✓	✓	✓	✓
Cancer-Related Fatigue (MFSI)		✓	✓	✓	✓	✓
Depression Symptoms (CES-D)		✓	✓	✓	✓	✓
Anxiety (STAI)		✓	✓	✓	✓	✓
Mood (POMS)		✓	✓	✓	✓	✓
Cognitive Problems (FACIT-COG)		✓	✓	✓	✓	✓
Quality of Life (FACIT)		✓	✓	✓	✓	✓
Pain (BPI)		✓	✓	✓	✓	✓
Pain (VAS)		✓	✓	✓	✓	✓
Leisure Time Physical Activity (GODIN)		✓	✓	✓	✓	✓
Daily Diary		✓	✓	✓	✓	✓
Feedback Questionnaire						✓
Qualitative Exit Interview						✓

Call Log		✓✓ 	✓	✓	✓	✓
Attendance Log				✓		

A second phone call is made at the end of baseline.

- 11.1 All written materials will be kept confidential, locked in the file room at the Research Base that is accessible only by Research Base personnel, and identified by study ID numbers. Electronic databases are password-protected with limited access.
- 11.2 Any treatment notes related to the study participant’s cancer treatment should be submitted with the baseline assessment.
- 11.3 The Case Summary should accompany ALL data submissions. Completed forms must be electronically submitted through the URCC Box upload system within 30 days of assessment time point
- 11.4 All electronic data collected, i.e., actigraphy files and video recordings must be stored on a HIPAA compliant, regularly backed up network storage or computer immediately after collection until notified by URCC to destroy it.

---

## 12.0 Gender and Ethnic/Racial Minorities

---

12.1 **Minority Groups or Subgroups:** This clinical trial is open to both women and men who are survivors of cancer.

An estimate of minority participation from our URCC Research Base accruals between 3/1/2011 and 2/29/2012 for three large phase III clinical trials in our target population of cancer survivors indicates minority participation will be approximately 13%. Our research group found 142 of the 1078 (13.17%) patients accrued to these clinical trials categorized themselves as being from an ethnic or racial minority. One of these studies was [name] recently completed phase III clinical trial testing the effects of an exercise intervention on cancer-related fatigue.

[name] has recently had success increasing minority accruals on her local single-site studies in Rochester, NY by implementing strategies suggested by the Recruitment and Retention Core of the URMC CTSI.

Male cancer patients have been underrepresented in yoga trials for cancer patients. In a systematic review and meta-analysis conducted in 2012, Buffart et al. found 13 published trials of yoga for cancer patients. Twelve of these trials focused specifically on breast cancer; 11 recruited only female patients, and one reported that 5% of their sample was male. The thirteenth trial was a small (N=38) pilot trial focused on lymphomas; 39% of this sample was male. In an analysis of population-based data, similarly, only 3.5% of men in the United States reported practicing yoga, compared to 10% of women.

To ensure sufficient representation of male cancer patients in the current trial, the following steps will be taken. Research coordinators at the NCORP sites will be instructed to screen specifically for and oversample male cancer patients in their recruitment efforts, to account for the potential reticence of men to engage in a group-based yoga intervention. Where possible, coordinators conducting recruitment will be gender matched to the patients they are recruiting (i.e., male coordinators recruiting male patients, female coordinators recruiting female patients). Recruitment and study materials, including study manuals include both male and female models.

For this study, our goal is to increase minority recruitment to 18% (a 5% increase). We will work closely with our minority-based NCORPs to ensure they have the resources and help they need to open this study and to effectively recruit participants and conduct the study. We will also work closely with our non-minority-based NCORPs to support increased minority accruals at all of our affiliated NCORPs. We will provide each NCORP with culturally

sensitive recruitment materials. Lastly, our IRB and all of our NCORP IRBs mandate that all study materials and measures meet federal guidelines and can be easily understood by individuals without a high school degree.

In addition, we will meet quarterly with Research Base staff and annually with all NCORPs; at face-to-face meetings and on audits where we will discuss minority recruitment levels and make adjustments in our recruitment strategies as needed in an earnest effort to increase minority recruitment for this trial.

Projected participation is shown below.

Racial Categories	Not Hispanic or Latino:	Not Hispanic or Latino:	Hispanic or Latino:	Hispanic or Latino:	Total
	Female	Male	Female	Male	
American Indian/Alaska Native	11	2	0	0	13
Asian	18	11	0	0	29
Native Hawaiian or Other Pacific Islander	8	7	0	0	15
Black or African American	43	22	5	1	71
White	483	80	17	5	585
More Than One Race	5	1	1	0	7
Total	568	123	23	6	720

---

